1.3.3. Overall Benefit:Risk Conclusion

For detailed information on the identified risks and benefit:risk assessment of retosiban, refer to the Investigator's Brochure (IB) [GlaxoSmithKline Document Number [CM2006/00201/06](#)]. The overall benefit:risk assessment of retosiban appears favorable for the mother and fetus/infant.

2. OBJECTIVES

The study objective is to assess the safety and outcomes in infants and children who were exposed to retosiban or comparator in the Phase III SPTL treatment studies. [Table 1](#) summarizes the specific study objectives and the corresponding endpoints, which are described in detail in Section [6.2](#) (Safety) and Section [6.3](#) (Health Outcomes).

Table 1 Summary of Study Objectives and Corresponding Endpoints

Objective	Endpoints
Primary	
 To characterize the clinical safety in terms of infant and child morbidity and mortality in infants and children exposed to retosiban or comparator in utero Proportion of infants and children with newly diagnosed (after 28 days post EDD) chronic medical conditions by type of condition will be recorded and include the following: 
 Respiratory conditions 
 Chronic lung disease Reactive airway disease Vocal cord paralysis Airway obstruction Neurological conditions 
 Cerebral palsy Seizure disorder Hydrocephalus requiring shunt Sensory conditions 
 Vision 
 Vision impairment Blindness in 1 or both eyes, or sees light only Hearing 
 Hearing impairment Deafness in 1 or both ears Hearing impaired, uncorrected even with aids Gastrointestinal conditions 
 GERD (moderate to severe) Tube/parenteral feeding Short bowel syndrome Cardiovascular conditions 
 Pulmonary hypertension Hypertension Renal conditions 
 Renal impairment requiring dialysis Growth parameters 
 Poor weight gain Reduced length Reduced head circumference Failure to thrive Proportion of infants and children with newly diagnosed (after 28 days post EDD) congenital anomalies Proportion of infant and child deaths that occur after 28 days post EDD and until 24 months chronological age

Objective	Endpoints
	
 • Neurodevelopment endpoints assessed at ages 9, 18, and 24 months, corrected for prematurity: 
 • Proportion of infants with an ASQ-3 score in the black zone in any domain • Proportion of infants with an ASQ-3 score in the black zone for gross motor skills • Proportion of infants with an ASQ-3 score in the black zone for fine motor skills • Proportion of infants with an ASQ-3 score in the black zone for communication • Proportion of infants with an ASQ-3 score in the black zone for problem-solving • Proportion of infants with an ASQ-3 score in the black zone for personal-social skills • Proportion of infants referred for developmental evaluation (using BSID-III) • Proportion of infants with a BSID-III score >2 SDs below the mean score for the cognitive scale (<4) • Proportion of infants with BSID-III score >2 SDs below the mean score for the gross motor scale (<4) • Proportion of infants with BSID-III score >2 SDs below the mean score for the fine motor scale (<4) • Proportion of infants with a BSID-III score >2 SDs below the mean score for the language scale (<70) • Proportion of infants with a CBCL/1.5-5 score above the 97th percentile for a subset of prespecified questions that relate to attention and hyperactivity problems • Proportion of infants indicated as needing further evaluation after completion of the M-CHAT-R/F • Proportion of infants referred for neurological evaluation to determine diagnosis of cerebral palsy • Proportion of infants with at least 1 of the following indicators of neurodevelopmental impairment: 
 • Hearing impaired, uncorrected even with aids (at 24 months chronological age) • Blindness in 1 or both eyes, or sees light only (at 24 months chronological age) • Cerebral palsy (moderate and severe) (at 24 months corrected age) • Cognitive impairment: BSID-III Cognitive Scale Score of >2 SDs below mean score (<4) (at 24 months corrected age) • Motor impairment: BSID-III Motor Composite Scale Score of >2 SDs below mean score (<70) (at 24 months corrected age) • Diagnosis of ASD, ADD, or ADHD

Objective	Endpoints
Exploratory To characterize parental productivity loss related to a sick child and infant resource utilization in terms of hospital admissions, length of stay, ER/UC visits, surgical procedures, and referral to specialty care or therapy visits for infants (up to age 2 years) exposed to retosiban or comparator in utero	
 Number of hospital admissions, proportion of infants and children with any hospital admission, post-birth hospitalization discharge, by principal and secondary discharge diagnosis, type of hospital unit admitted to (e.g., NICU, Pediatric, PICU, Nursery level 3, ICU), and length of hospital stay per unit after 28 days post EDD and until 24 months chronological age Combined length of hospital stay in days for all hospital admissions (for infants discharged from the delivery hospitalization and for babies who were never discharged home post-delivery) after 28 days post EDD and until 24 months chronological age Number of surgical procedures (details of type and whether performed on an inpatient basis or at an outpatient/surgical center will be collected up to 24 months chronological age only) after 28 days post EDD and until 24 months chronological age Number of ER/UC visits and proportion of infants with any ER/UC visit after 28 days post EDD and up to 24 months chronological age Number of specialty care or therapy visits and proportion of infants referred for specialty care or therapy by type of care/therapy after 28 days post EDD and up to 24 months chronological age Parental productivity loss related to infant hospital admissions, ER/UC visits, or specialist care after 28 days post EDD and up to 24 months chronological age

ADD = attention deficit disorder; ADHD = attention deficit hyperactivity disorder; ASD = autism spectrum disorder; ASQ-3 = Ages and Stages Questionnaire-3; BSID-III = Bayley Scales of Infant Development, third edition; CBCL/1.5-5 = Child Behavior Checklist for Ages 1.5 to 5; EDD = estimated date of delivery; ER/UC = emergency room/urgent care; GERD = gastroesophageal reflux disease; ICU = intensive care unit; M-CHAT-R/F = Modified Checklist for Autism in Toddlers-Revised with Follow-Up; NICU = neonatal intensive care unit; PICU = pediatric intensive care unit.

[figure not shown]
3. INVESTIGATIONAL PLAN

3.1. Study Design

ARIOS is a long-term infant and child follow-up study that will prospectively assess safety and outcomes of all infants and children born to women who received at least 1 dose of retosiban or comparator in any of the Phase III SPTL treatment studies. The final assessment of the Phase III SPTL treatment studies is a collection of neonatal morbidity data and will occur at 28 days after the EDD, where EDD is defined as 40^{0/7} weeks' gestation. The end date of the Phase III SPTL treatment studies is referred to as 28 days post EDD. Either the obstetrician investigators or neonatologist subinvestigators from the Phase III SPTL studies or their delegate will be responsible for obtaining consent for the infant to participate in the follow-up study; they also will be responsible for obtaining the signed medical release forms from all hospitals and HCPs providing follow-up care to the infant. Ideally, the Phase III SPTL study investigators will obtain

consent and medical release when the woman's acute episode of preterm labor has resolved and prior to discharge from the hospital for the treatment of preterm labor. The infant will be allowed to be consented into the study until the later date of either the date of discharge from the birth hospitalization or up to 9 months corrected age (to allow for the infant's 9-month Child Health Inventory [CHI] and ASQ-3 data collection) via follow-up contact from the research coordinating center-principal investigator (RCC-PI) to the parent/legal guardian. This follow-up contact and informed consent discussion may occur via telephone with signed consent and medical releases transmitted via mail or courier. Infants and children will be followed at prespecified intervals until they reach 24 months chronological age (see [Table 2](#)). This study does not require medical interventions or study visits to an investigational site. Instead, parents or legal guardians will be prompted at certain time points to complete developmental questionnaires and other data on their children's health status via an electronic device. Data collected during this follow-up study will be managed by a centralized RCC. Regionally based pediatricians will serve as study principal investigators (referred to as RCC-PIs) for this study. All communications the RCC-PI has with the parent/legal guardian or the child's HCP will occur remotely; there will be no clinic visits. An overview of the study design is shown in [Figure 1](#).

Figure 1 **Study Design**

EDD = estimated date of delivery; HCP = health care provider; RCC = research coordinating center; RCC-PI = research coordinating center-principal investigator; SPTL = spontaneous preterm labor.

Electronic data capture (eDC) tools and processes including electronic case report forms (eCRF) and electronic patient-reported outcome devices will allow entry of data, regardless of when it is obtained. If at any time the data suggest any developmental delay, the RCC-PI will refer the child to a specialist (if not already under the care of a specialist) for formal evaluation and additional assessments. The child's local primary care pediatric

provider will be asked to provide routinely available data on the child to the RCC. Additional contacts may occur at the discretion of the RCC personnel to complete the data collection.

The child's parent/legal guardian will be asked to complete the CHI at 2, 6, 9, 12, 15, 18, 21, and 24 months of the child's chronological age. The CHI questionnaire completed up to the 24-month time point will screen for infant mortality and morbidity and will capture data on resource utilization. If the parent/legal guardian indicates that the child has been newly diagnosed (after 28 days post EDD) with chronic conditions or congenital anomalies, follow-up will be undertaken with the applicable HCP to confirm the parent/legal guardian report. Persistence or resolution of conditions will be determined in subsequent questionnaires after the initial report. If protocol-specific evaluations are in progress at the end of the child's protocol-defined participation in this study (24 months chronological age) and results have not yet been received or reported, the time period may be extended to collect those reports.

If the parent/legal guardian indicates that the child has had any emergency room/urgent care (ER/UC) visits, he/she will be asked to record the number of visits and to indicate if the visit resulted in hospitalization. If the parent/legal guardian indicates that the child has been hospitalized or has had any surgeries, medical records from the applicable medical facility will be obtained and abstracted for pertinent details, including principal and secondary discharge diagnoses, type of hospital unit admitted to (e.g., neonatal intensive care unit [NICU], Pediatrics, pediatric intensive care unit [PICU], Nursery level 3, ICU), and length of stay. If the parent/legal guardian indicates that the child died after 28 days post EDD, details of the death will be obtained from the death certificate or appropriate HCP or medical records if the death certificate is not available. Note that all infant deaths that occur before 28 days post EDD will be captured and reported as part of the Phase III SPTL treatment studies.

During the 24 months of participation in the study, if the parent/legal guardian indicates that the infant has been treated by specialists or has had ER/UC visits or hospitalizations, he/she will be asked to complete a productivity questionnaire to evaluate loss of parental productivity.

The RCC-PI will review all data including medical records, death certificates, data provided by the parent/legal guardian, and any follow-up confirmatory data provided by HCPs. The RCC-PI may request targeted follow-up data from the relevant HCP or medical facility if clarification is needed on any reported study endpoints or SAEs.

When a congenital anomaly is reported, it will be reviewed by an expert in teratology who is engaged by the RCC-PI to serve as the birth defect evaluator for this study. The birth defect evaluator's responsibilities will include the review, evaluation, and classification of all reports of birth defects.

To screen for developmental issues, the parent/legal guardian will be asked to complete the 9-, 18-, and 24-month ASQ-3 when the infant's corrected age corresponds to 9, 18, and 24 months, for example, parents/legal guardians of an infant born 3 months premature will complete the 9-month ASQ-3 at 12 months chronological age. Any child

who scores in the black zone (≥ 2 SD below the mean) (see Section 6.2.5.1) in any of the 5 domains of the ASQ-3 will be referred to a qualified assessor for a developmental evaluation (e.g., using the Bayley Scales of Infant Development, third edition [BSID-III]), and a neurologic examination will be conducted, if indicated. An overall assessment of delay in the areas of communication, gross and fine motor, problem-solving, and personal-social development will be rendered. As part of normal management, some infants may already have undergone a formal developmental evaluation using the BSID-III; in these cases, if testing was recent (≤ 3 months), the BSID-III will not be repeated and RCC-PI will request results from the relevant HCP. BSID-III retesting will be requested if the child's ASQ-3 scores are in the black zone on a subsequent ASQ-3 test following the first BSID III referral. Based on results from the ASQ-3 administered at 24 months corrected age and if no cerebral palsy diagnosis has been made to date (see Section 6.2.5.1), the infant may be referred to a qualified examiner for a formal assessment of cerebral palsy.

The M-CHAT-R/F will be completed for all infants at 18 and 24 months (corrected age) and the CBCL/1.5–5 will be completed for all infants at 24 months (corrected age) to assess the risk for other behavioral problems or autism spectrum disorder (ASD). If at any of these time points a child has an M-CHAT-R/F score that indicates further evaluation is required and/or a CBCL/1.5–5 score above the 97th percentile for a subset of prespecified questions, the child will be referred to a specialist for a formal assessment.

Protocol Amendment 2 has updated the total study duration to 24 months. Babies or infants that have passed the 24-month assessments after the amendment implementation are not required to continue further within the study, nor do they need to complete any subsequent study-related assessments. Following completion of the study, the neonates will continue their normal pediatric standard of care with their primary care pediatrician or health care provider.

The 24-month data will form the final study endpoint assessment timing; however, if data have been collected from a baby/infant after they have passed the 24-month endpoint, then this data will be included as a data listing within the clinical study report.

Data and genetic samples from the Phase III SPTL treatment studies may be used as part of a genetic analysis using data collected in this study, if relevant. No additional genetic samples are required.

Protocol waivers or exemptions are not allowed with the exception of immediate safety concerns. Therefore, adherence to the study design requirements, including those specified in the Time and Events Table (Table 2), are essential and required for study conduct. All specified completion windows for applicable questionnaires (CHI, ASQ-3, CBCL/1.5–5, M-CHAT-R/F, and productivity) are provided to help standardize the data and avoid overlap. Information captured outside of these windows will be collected and analyzed separately, and questionnaires completed outside the completion window will not be considered protocol deviations.

Supplementary study conduct information not mandated to be present in this protocol is provided in the accompanying Study Procedures Manual (SPM). The SPM will provide the site personnel with administrative and detailed technical information that does not impact subject safety.

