6. STUDY ASSESSMENTS AND PROCEDURES

The child's parent/legal guardian will be the primary data reporter to the study. Confirmation of key study endpoints will be obtained from applicable HCPs or health care facilities. The infants and children will be followed beginning from after 28 days post EDD and until 24 months chronological age. Baseline characteristics and demographic data will be captured from the Phase III SPTL treatment studies and combined with child follow-up data for analyses. Refer to [Table 2](#) for a summary of data points to be collected and the time frame for assessment.

The time points for parent-completed questionnaires are scheduled to maintain the participant's interest in study continuation and minimize losses to follow-up. Questionnaires will be associated with the child's age; in some cases, the age will be chronological and in other cases, it will be corrected for prematurity. The timing of the first questionnaire is scheduled to begin at 2 months chronological age and end at 24 months chronological age. Contingent on the infant's chronological age at the time of entry into the follow-up study, all of the questionnaires may not be completed for each participant. The SPM will provide explicit details on study procedures to ensure proper timing of questionnaires.

It is noted that as part of the Phase III SPTL treatment studies, the infant's mother will be asked to complete the Edinburgh Postnatal Depression Scale (EPDS) using the same eDC

system as will be utilized for this study. The EPDS should ideally be completed at 6 weeks (-2 weeks/+6 weeks) post-delivery but may be completed as early as 4 weeks post-delivery or as late as 12 weeks post-delivery. While the timing for EPDS may fall into the time period for this study, data will be captured as part of the Phase III SPTL treatment study, and the SPTL treatment study investigator will be responsible for reviewing information and any action required. As such, the EPDS is not reflected in [Table 2](#). The SPM will provide details on the EPDS completion and process.

Table 2 Time and Events Table

Event	28 Days Post EDD	Months							
		2	6	9	12	15	18	21	24
Written informed consent ¹		←	→						
Baseline characteristics and demographic data	X ²								
RCC confirms and updates contact information from the parent/legal guardian	X								
Parent/legal guardian completes CHI ³		X	X	X	X	X	X	X	X

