RCC-PI follows up with HCP and reviews medical or other records to confirm parent-reported outcomes									→
RCC-PI reviews CHI results and refers to birth-defect evaluator based on results									→
Parent/legal guardian completes productivity questionnaire ⁴									→
Parent/legal guardian completes ASQ-3 ⁶				X ⁵			X ⁵		X ⁵
RCC-PI reviews ASQ-3 results and refers for developmental evaluation based on results ⁶									→
Parent/legal guardian completes M-CHAT-R/F ⁷							X		X
Parent/legal guardian completes CBCL/1.5–5 ⁷									X
RCC-PI refers child to specialist for cerebral palsy assessment (if required) ⁸									X

ASQ-3 = Ages and Stages Questionnaire-3; CBCL/1.5–5 = Child Behavior Checklist for ages 1.5 to 5; CHI = Child Health Inventory; EDD = estimated date of delivery; HCP = health care provider; M-CHAT-R/F = Modified Checklist for Autism in Toddlers-Revised with Follow-Up; RCC = research coordinating center; RCC-PI = research coordinating center-principal investigator.

Note: All specified completion windows for applicable questionnaires (CHI, ASQ-3, CBCL/1.5–5, M-CHAT-R/F, and productivity) are provided to help standardize the data and avoid overlap. Information captured outside of these windows will be collected and analyzed separately, and questionnaires completed outside the completion window will not be considered protocol deviations.

1. Collected at the start of the Phase III spontaneous preterm labor (SPTL) treatment studies until the later date of either the date of discharge from the birth hospitalization or up to 9 months corrected age (to allow for the infant's 9-month CHI and ASQ-3 data collection).
2. Captured in Phase III SPTL treatment studies and combined with child follow-up data for analyses.
3. A positive response by the parent/legal guardian may trigger follow-up with the relevant HCP and/or medical record review for confirmation or more details on the condition or hospitalization. At each time point, the completion window of the CHI is +6 weeks.
4. Completed if infant has been treated by a specialist or has had an emergency room/urgent care or hospital visit. The completion window for the productivity questionnaire is +2 weeks from the date of completion of the relevant CHI.
5. Based on infant's corrected age. The completion window for the ASQ-3 is +30 days at Month 9 and \pm 30 days at Months 18 and 24.
6. If the parent/legal guardian receives a referral, then a qualified specialist will complete required assessments.

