9.5. Study and RCC Site Closure

Recruitment in participating countries will begin with initiation of the Phase III SPTL treatment studies. Recruitment will continue until the Phase III SPTL treatment studies end recruitment. Follow-up will continue until each child enrolled completes the 24-month questionnaire at 24 months chronological age. For any subject that was enrolled prior to Amendment 2, those subjects who have completed the 24 months assessments will not be required to complete the CHI questionnaire at 3, 4, and 5 years of the child's chronological age. Study close-out and final reporting activities will be initiated on completion of the follow-up on the last study participant.

Upon completion or termination of the study, the PPD monitor will conduct RCC site closure activities with the RCC-PI or RCC site staff (as appropriate), in accordance with applicable regulations, GCP, and GSK/PPD Standard Operating Procedures.

GSK reserves the right to temporarily suspend or terminate the study at any time for reasons including (but not limited to) safety issues, ethical issues, or severe noncompliance. If GSK determines that such action is required, GSK will discuss the reasons for taking such action with the RCC-PI. When feasible, GSK will provide advance notice to the RCC-PI of the impending action.

If any study with retosiban is suspended or terminated, GSK/PPD will promptly inform all RCC-PIs. GSK/PPD will also promptly inform the relevant regulatory authorities of the suspension/termination along with the reasons for such action. Where required by applicable regulations, the RCC-PI must inform the IRB/IEC promptly and provide the reason(s) for the suspension/termination.

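### The protocol ends participation at 24 months chronological age, 22 to 112 days before preterm infants reach the 24 months corrected age at which the final neurodevelopment assessments fall due

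*Protocol*

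**What the plan says.** **Chronological end.** Besides the sentence in Protocol 3.1 ("Infants and children will be followed at prespecified intervals until they reach 24 months chronological age"), which points to Table 2, the same section puts the end of protocol-defined participation at 24 months chronological age in its extension clause. Section 6 says of the questionnaires: "The timing of the first questionnaire is scheduled to begin at 2 months chronological age and end at 24 months chronological age". Section 9.5 says: "Follow-up will continue until each child enrolled completes the 24-month questionnaire at 24 months chronological age". The Protocol Summary and 8.3.4 repeat this end.

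**Corrected-age assessments.** In Protocol 3.1 the parent is "asked to complete the 9-, 18-, and 24-month ASQ-3 when the infant's corrected age corresponds to 9, 18, and 24 months". For autism screening, "The M-CHAT-R/F will be completed for all infants at 18 and 24 months (corrected age"); the CBCL/1.5-5 follows at 24 months corrected age. Table 2, footnote 5, on the ASQ-3, reads: "Based on infant's corrected age. The completion window for the ASQ-3 is +30 days at Month 9", and gives 30 days either side at Months 18 and 24. Footnote 7 gives the M-CHAT-R/F and CBCL a window of +12 weeks at 24 months, with no early side. Section 6.2.6 sets the cerebral palsy, cognitive and motor components at 24 months corrected age, and hearing and blindness at 24 months chronological age.

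**SAP.** Sections 2.2 and 7.2.3 use corrected age for the neurodevelopment endpoints. The general wording varies. Sections 1 and 2.3 say corrected age, or chronological age if applicable. Section 7.2 cuts at 24 months chronological age where appropriate. Sections 2.4, 4 and 6.2 refer to 2-year assessments without an age basis, and 2.4 and 4 keep later data out of the summaries.

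**The concern.** Both rules stand in the current text and cannot both be followed for a preterm infant. Protocol 3.1 makes adherence to Table 2 mandatory, so the corrected-age schedule is binding. The end of participation is stated just as plainly.

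At stake are primary endpoints of a safety study whose stated goal is assurance about early childhood outcomes. If the chronological end were applied, the last screening round would not be collected in window. The BSID-III and cerebral palsy referrals that the 24-month ASQ-3 triggers would not arise either. The gap is longest for the earliest births, and Protocol 1.3.2 gives babies born before 32 weeks the greatest risk of death and poor health outcomes.

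There is a possible second step. SAP 10.6.2 assumes that events did not occur where safety or neurodevelopment data are missing. If uncollected 24-month results were handled that way, the reported proportions could only fall.

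**Working it through.** **Inputs**
- Corrected age: chronological age minus the time born before 40+0 weeks, i.e. 280 days (Protocol, Definitions).
- Earliest birth considered: 24+0, the lowest gestational age for maternal entry (Protocol 1.1.1).
- Latest preterm birth: 36+6, since preterm means before 37 completed weeks (Protocol 1.1).
- Windows at 24 months: ASQ-3 ±30 days; M-CHAT-R/F and CBCL +12 weeks (84 days); CHI +6 weeks (42 days) (Table 2 footnotes; 6.2.1.1).

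**Plan's own figure.** Protocol 3.1 says an infant born 3 months premature completes the 9-month ASQ-3 at 12 months chronological age: 9 + 3 = 12, reproduced. The same sum for the last ASQ-3 is 24 + 3 = 27 months, 3 months after the stated end.

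**Formulas** (days after 24 months chronological age)
- Gap = 280 − gestational age at birth in days.
- ASQ-3 window: gap − 30 to gap + 30.
- M-CHAT-R/F and CBCL window: gap to gap + 84.

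| Birth (weeks+days) | Days | Gap | ASQ-3 window | M-CHAT-R/F and CBCL window |
|---|---|---|---|---|
| 24+0 | 168 | 112 | 82 to 142 | 112 to 196 |
| 28+0 | 196 | 84 | 54 to 114 | 84 to 168 |
| 31+6 | 223 | 57 | 27 to 87 | 57 to 141 |
| 34+0 | 238 | 42 | 12 to 72 | 42 to 126 |
| 35+4 | 249 | 31 | 1 to 61 | 31 to 115 |
| 35+5 | 250 | 30 | 0 to 60 | 30 to 114 |
| 36+6 | 258 | 22 | −8 to 52 | 22 to 106 |

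At the stated end (day 0), the M-CHAT-R/F and CBCL windows are unopened for every preterm birth. The ASQ-3 window is unopened for births at 35+4 or earlier.

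**Lenient end.** Suppose the end is stretched to the close of the 24-month CHI window (day 42).
- ASQ-3 is unopened if gap − 30 > 42, i.e. gap > 72: births at 29+4 (gap 73) or earlier.
- M-CHAT-R/F and CBCL are unopened if gap > 42: births at 33+6 (gap 43) or earlier.

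**Does other text settle it?**
- The extension clause begins "If protocol-specific evaluations are in progress at the end of the child's protocol-defined participation in this study (24 months chronological age") and covers only evaluations already under way with results outstanding. A questionnaire not yet due is not under way, nor is a referral it would have triggered.
- The release rule reads: "Babies or infants that have passed the 24-month assessments after the amendment implementation are not required to continue further within the study". It gives no age basis for those assessments.
- Extra contacts (3.1) are at the coordinating center's discretion.
- Early completion does not help: Protocol 3.1 has out-of-window information analyzed separately.

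**The case against.** The strongest reply is that specific text governs general text. Every instrument-level statement uses corrected age, the sentence ending follow-up refers to Table 2, and Table 2 is mandatory. Section 6 also says that some questionnaires follow chronological age and others corrected age, and leaves timing detail to the Study Procedures Manual. On that reading a site that stopped at 24 months chronological age would breach the protocol, so loss of data is not the natural outcome.

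This stands in part: the intended schedule is probably the corrected-age one. It does not cure the text. Section 6 mentions both age bases and in its next sentence still ends the questionnaires at 24 months chronological age. Protocol 3.1 calls the manual supplementary, and it is not among the documents.

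Two stronger readings should be set aside.
- A reader might infer that the SAP contradicts itself on the neurodevelopment endpoints. It does not: 2.2 and 7.2.3 use corrected age, and deaths (2.2) and SAEs (7.2.2.1) have their own chronological cut. A summary limit worded by assessment can naturally include the corrected-age round.
- A reader might infer that SAP 10.6.2 will turn the lost results into non-events. That section describes missing data as requested data not provided. Whether it reaches questionnaires never requested, or data collected but only listed, is itself unclear.

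**Conclusion.** Wrong as written. The stated end of participation precedes assessments that the protocol requires, by 22 days (birth at 36+6) to 112 days (birth at 24+0). The upper figure is an extreme case: it needs delivery at the lowest gestational age for maternal entry. The lower figure takes preterm as before 37+0; applied literally to births from 37+0 to 39+6, the formula adds gaps of 1 to 21 days.

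The harm is conditional on the end rule being followed literally, and is confined to the 24-month corrected-age endpoints. The 9- and 18-month assessments are untouched. In the composite, hearing, blindness, a diagnosis of ASD, ADD or ADHD, and cerebral palsy diagnosed earlier can still count.

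The number of infants affected cannot be computed, because gestational ages at birth are not given. A reader might take 98 − 34 = 64, the enrolled infants who had not completed 24 months at the June 2018 data cut (Appendix 1, Amendment 2), as the number at risk. The documents do not support that: the 64 may include term births, withdrawals, and infants who reached 24 months corrected age while 5-year follow-up still applied. Nothing in the documents supports an estimated effect on reported rates, or bias between arms.

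**What to change.** **Protocol Summary, 3.1, 6, 8.3.4 and 9.5.** Define the end of participation as the later of 24 months chronological age and completion of the 24-month corrected-age questionnaires within their windows, with any evaluations they trigger. All five places need the change, or the contradiction remains.

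**Protocol 6.2.4, 6.2.10 and 6.2.11.** State explicitly whether death and SAE collection still stops at 24 months chronological age once participation runs past it.

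**SAP 1, 2.3, 2.4, 4, 6.2 and 7.2.** Define the 2-year assessment as including the 24-month corrected-age assessments and their windows, so that these are summarised and not only listed. Limit the chronological cut to deaths, SAEs, CHI-based endpoints, and the hearing and blindness components.

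**Cost.** Wording, plus remote follow-up that Table 2 already implies. For a birth at 24+0 the windows close 142 days (ASQ-3) and 196 days (M-CHAT-R/F and CBCL) after 24 months chronological age, plus time for any triggered evaluation. No clinic visits to an investigational site are added.
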